# 5.2 Pre-procedure preparation and safety screen

The proceduralist will explain the ESPB to the patient and answer all questions while obtaining informed consent. After this, the proceduralist and assistants will obtain all nerve block supplies, a department ultrasound system, and properly position the patient. The proceduralist will also ensure that appropriate monitoring equipment (telemetry and pulse oximetry) is in place, primary provider team and primary beside nurse are informed of the procedure, and local anesthetic is obtained from the ED pharmacy. The proceduralist will calculate the maximum safe dose of local anesthetic for the patient. The long-acting local anesthetic to be used in this study is 0.5% Ropivacaine (5 mg/mL) for which the maximum safe dose is 3 mg/kg in 8 hours. The dose will be calculated based on patient weight with a maximum dose of 150 mg (30 mL). Peripheral nerve block is considered on-label use of ropivacaine and the study dose (up to 150 mg) and volume (30 mL) are within the suggested ranges of the approved label. The proceduralist will also confirm the patient does not have allergy to local anesthetic. The proceduralist will also ensure availability of lipid emulsion (Intralipid) in the ED pharmacy. Intralipid is a medication used to treat local anesthetic systemic toxicity (LAST) and would only

be administered in the event of development of LAST. A study team member other than the proceduralist (coordinator or other investigator) will perform a pre-procedure assessment of pain using the visual analog scale. All pre-procedure preparation elements, assessment of pain, and re-confirmation of eligibility criteria will be recorded as the safety screen checklist in the REDCap database.

# 5.3 Erector spinae plane block

The ESPB is a peripheral nerve plane block routinely performed by emergency physicians for a variety of painful conditions and has been previously described in detail. This plane block will be performed as a "single-shot" using a long-acting local anesthetic. Briefly, a timeout will be performed, the correct patient identification, indication, procedure, and laterality will be confirmed. The proceduralist will review the maximum safe dose of local anesthetic and draw up 30 mL of 0.5% ropivacaine (150 mg) into a sterile syringe. No adjunct medications will be used. If the patient's calculated maximum safe dose results in a volume of less than 30 mL, the maximum safe dose will be diluted in sterile normal saline to achieve 30 mL total volume. With the patient in the sitting, decubitus or prone position per the patient's preference, ultrasound will be used to identify the transverse spinous process at the level of T8 and this site will be marked. The injection site and technique have all been previously used in a clinical trial for the same indication. A hair covering, mask, eye protection and sterile gloves will be donned. The site will be cleaned with chlorhexidine solution and allowed to fully dry. ESPB will be performed with sterile technique using in-plane ultrasound guidance. After administration of local anesthetic, the proceduralist will clean the site and apply a bandage. The proceduralist will document a research visit note in the EHR that indicates time the ESPB was performed, immediate complications, recommended actions if complication, and contact information for the study team.

# 5.4 Post-procedure assessment

Immediately after the procedure, the proceduralist will assess for immediate complications with the patient and inform the primary care team as well as the patient of the expected time course for effective analgesia. At one hour after the procedure, a study team member other than the proceduralist will reassess pain with the patient using the visual analog scale. The study team will also inquire as to preferences for follow up assessment (if the participant has opted in). These data will be recorded into the electronic case report form (ECRF) as the post-procedure assessment

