# 2.9 Secondary and exploratory outcomes

 Difference in visual analog scale pain (1-10) from prior to procedure to first pain assessment after 60 minutes from completion of ESPB as assessed by bedside nurse

- ED operational metrics admission to hospital, rate of 72-hour return to ED and length of stay
- Opioid pain medication usage measured in intravenous morphine equivalents and proportion of patients that receive a prescription for opioid pain medication
- Survey follow-up administered online with/without telephone assistance at 1, 7 and 30 days from initial ED visit (days 1, 7 are optional and on day 30 pain medication use questions are optional)
- Frequency of prespecified complications related to ESPB

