# 3.2 Erector spinae plane block for urolithiasis

The ESPB was first described in 2017 and has gained popularity for its utility as a safe and effective pain control modality for a variety of surgical procedures including abdominal, breast, thoracic and lumbar spine surgery. The ESPB provides analgesia by inhibiting neurotransmission at the dorsal and ventral rami of the thoracic spinal nerves, providing anesthesia to multiple dermatomal levels. 17 The ESPB is especially suited for renal colic because epidural spread has also been noted for local anesthetic agents leading to both visceral and somatic analgesia. 18 The technique has been shown effective for treating the pain associated with percutaneous nephrolithotomy as well. 19 The procedure has also been adopted in the Emergency Department for treating pain from rib and spinous process fractures, herpes zoster, and acute pancreatitis. 20-24 Recent case series described use of the ESPB for treatment of renal colic. Aydin et al. performed a pilot randomized trial of 40 patients evaluating ESPB performed by emergency physicians against non-steroidal anti-inflammatory drugs for renal colic and found that patients in the ESPB group had significantly lower opioid consumption and pain scores measured on a visual analog scale. Of note, patients receiving ESPB in this study had no opioid medication use after the procedure. Likewise, Noble et al. reported a case series of 10 patients whose renal colic was treated with ESPB and concluded that within 30 minutes of the procedure, most patients had total or significant reduction in their pain and that the ESPB was effective in those patients with opioid use disorder. Importantly, in both these studies, no significant complications of the procedure were reported.

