# 3.5 Study Aims

- Determine the efficacy of the erector spinae plane block performed by emergency physicians for the treatment of pain related to uncomplicated urolithiasis
- Determine the effect of ESPB on ED operations metrics (disposition, length of stay, return to ED)
- Determine the effect of ESPB on use of opioid medications in the ED and during the follow up period

Estimate rate of complications for ESPB when performed by EPs

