#### 3.6.2 Secondary Outcomes

- Difference in visual analog scale pain (1-10) from prior to procedure to first pain assessment after 60 minutes from completion of ESPB assessed by bedside nurse
  - Historic data from the U-M ED suggests that the median maximal pain reduction (last pain score minus first) in the ED is a mean reduction of 3.4 points (SD = 3.0) from a starting value of 7.9.
- ED operational quality metrics:
  - o Rate of admission to hospital
  - Rate of 72-hour return to the ED
  - ED length of stay
- Safety outcomes and complications at day 30

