#### 8 RISK ASSESSMENT

# 8.1 Potential Risk to Subjects

This study is a single treatment arm trial of ESPB for uncomplicated renal colic to investigate efficacy and complications. Prior studies did not report any major or minor complications as a result of ESPB performed by emergency physicians. However, in prior studies performed perioperatively by anesthesiologists, the following complications were identified: local anesthetic toxicity or allergy, infection or bleeding of the soft tissue overlying the needle insertion site, vascular puncture, pneumothorax, and failed block. Based on prior literature, complications are considered extremely rare because the potential space superficial to the T8 transverse process (site of injection to create plane block) is far from the spinal cord, pleura and major blood vessels. Additional risks to participants include risk of delay in care or other analgesia medication as well as temporary discomfort (lasting less than 1 hour) due to the procedure. Additional risks to both participants and external controls (whose data is secondarily collected from EHR query) are loss of confidentiality.

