#### 8.6.3 Adverse Events

The following serious adverse events (SAE) have been predefined: 1) death as a result of procedure complication; 2) hospitalization or prolongation of hospitalization as a result of

procedure complication; 3) permanent neurovascular injury; 4) pleural or vascular injury requiring surgical intervention; 5) infection at site of procedure; 6) development of anaphylaxis or local anesthetic systemic toxicity after procedure. There may be other unanticipated adverse events which include potential adverse events related to ropivacaine administration These adverse events are listed in Table 3A of the ropivacaine package insert. Please note that the AEs listed here are for regional anesthesia when performed in the intra- and peri-operative settings and with continuous infusion rather than single-shot administration.

All adverse events that occur will be logged centrally and reported to the IRB.

The PI or other study team member will promptly report the following events to the IRB if the events occur within 30 days of participation in the study: 1) any change in the study taken without prior IRB review; 2) interim findings that indicate an unexpected change to the risks or potential benefits of the research; 3) publications that indicate an unexpected change to the risks or potential benefits of the research; 4) serious adverse event as listed above.

Annual reports will be submitted to the local IRB if needed. Reports will contain a summary of all adverse events that occurred since the last IRB review.

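### After the check made straight after injection, no complication question has a set time in the ED, so uncharted mild or moderate events may be under-counted

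*Combined protocol and SAP*

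**What the plan says.** Section 3.5 lists as an aim: "Estimate rate of complications for ESPB when performed by EPs". Section 2.9 turns this into an outcome, "Frequency of prespecified complications related to ESPB", and section 3.6.2 gives a secondary outcome, "Safety outcomes and complications at day 30". Section 3.6.3 adds immediate complications as an exploratory outcome, without a time window.

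For the ED visit, section 5.4 says: "Immediately after the procedure, the proceduralist will assess for immediate complications with the patient". At one hour, "a study team member other than the proceduralist will reassess pain with the patient using the visual analog scale", and the team also asks about follow-up preferences. Section 6.2 mentions only pain at that time. Section 8.2 has the same pattern: complications straight after the block, pain at 60 minutes.

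The plan also has broader provisions. Section 5.2 puts telemetry and pulse oximetry in place and has the bedside nurse and treating team told of the procedure. Section 8.6.2 makes physician investigators responsible for adverse event collection during the index visit, draws on all data sources including the EHR, and gives participants a route for self-report. Sections 5.5 and 6.3 ask about complications at days 1, 7 and 30, and only the day-30 question is mandatory.

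Among the events of interest, section 8.6.3 predefines as serious "development of anaphylaxis or local anesthetic systemic toxicity after procedure", and section 8.1 names "vascular puncture, pneumothorax, and failed block" among known complications.

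**The concern.** A complication rate is only as good as the looking behind it. Here the one complication check with a stated time comes before some of the named events can be judged. Failed block is the clear case. Section 3.2 reports from a case series that "within 30 minutes of the procedure, most patients had total or significant reduction in their pain", so lack of effect cannot be assessed when the needle comes out. The toxicity event in 8.6.3 is described as arising after the procedure and is not tied to the moment of injection.

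At one hour a team member is at the bedside with a form open, but the text gives that person no complication question to ask. If the trial then reports few or no complications, the figure could be read as evidence of safety, although capture after the first check was unstructured.

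**Working it through.** **Step 1: set out the contacts.**

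| Time | Source of information | Complications asked about? | Status |
|---|---|---|---|
| Straight after the block | Proceduralist (5.4, 8.2) | Yes | Scheduled |
| 1 hour | Someone other than the proceduralist (5.4, 6.2); the proceduralist (8.2) | Not listed; pain and follow-up preferences only | Scheduled |
| Rest of ED visit | Physician investigators, EHR, self-report (8.6.2) | Yes, but no times or items | Unscheduled |
| Days 1 and 7 | Survey (6.3) | Yes | Optional |
| Day 30 | Survey or telephone call (5.5, 6.3) | Yes | Mandatory |

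A participant who declines the sub-study therefore has no scheduled complication question between the first check and day 30.

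**Step 2: ask what the unscheduled routes would pick up.**

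- Section 8.6.2 gives index-visit collection to physician investigators and mentions other staff only for the follow-up period. Under 6.2 the one-hour assessor may be a coordinator, who then has no stated adverse event task.
- The EHR variables in 6.4 include diagnoses, procedures and medications, but no symptom or adverse event field. Manual chart review is done only if needed.
- Section 8.6.6 defines grade 1 as needing no treatment. Such an event may leave no order, diagnosis or drug record, yet 8.6.3 requires every adverse event to be logged.
- Section 5.2 states no duration for telemetry and oximetry, and no route from them to the case report form.

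Treated or serious events would probably surface. Mild or moderate events without a chart entry may not.

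**Step 3: failed block.** It is in the list in 8.1, absent from the predefined serious events in 8.6.3, and defined nowhere. The one-hour pain score and the primary outcome (a second parenteral pain medication) both bear on it, so data exist. What is missing is a rule that turns them into a count.

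**Step 4: scale.** The plan states no expected complication rate, precision target or capture rate, so there is no safety figure to reproduce. The Simon design in 2.10 does reproduce (18 at interim, 54 in total, stop at 10 or fewer responders of 18) and is untouched by this point.

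The treated target is 60 (2.10). With no events, the exact one-sided 95% upper limit is

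1 − 0.05^(1/60) = 0.0487, or 4.9%.

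This assumes that every event is found. If a fraction s is found, independently of other events, the recorded rate is s times the true rate, and the limit on the true rate is 0.0487/s:

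- s = 0.75 (assumed): 0.0487/0.75 = 6.5%
- s = 0.50 (assumed): 0.0487/0.50 = 9.7%

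The chance of recording at least one event in 60 patients is 1 − (1 − rate × s)^60:

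| Assumed true rate | s = 1 | s = 0.75 | s = 0.50 |
|---|---|---|---|
| 1% | 45% | 36% | 26% |
| 2% | 70% | 60% | 45% |
| 5% | 95% | 90% | 78% |

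These figures show how the result depends on capture. They do not estimate this trial's capture.

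**The case against.** The strongest reply is that the complication rate does not rest on the first check. The secondary safety outcome is set at day 30, and immediate complications are only exploratory. Section 8.6.2 covers the whole index visit, uses every data source and invites self-report. The patient is monitored, the treating team knows of the block, and 8.6.4 sets out how events during the encounter are reported. This stands for serious events. A reader might infer that the plan misses toxicity arising later in the visit, and the documents do not support that. What they show is capture without a schedule, which may be incomplete for minor events.

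A reader might also infer that failed block goes unobserved. It does not, for the reason given in step 3. Nor does the limit of 3 mg/kg in 8 hours in 5.2 show that toxicity is expected over 8 hours. It is a dose ceiling, and the documents give no onset time for toxicity.

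It can also be said that 5.4 and 6.2 never limit the one-hour contact to pain, that 5.1 speaks of data collection at one hour without restriction, and that the workflow figure (Figure 1B) and the case report form might hold more. Neither was available for this review. If they carry complication items, the remedy is to bring the text into line. As the text stands, no such item is required.

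**Conclusion.** The point holds in a limited form. The only complication check with a set time in the ED is the one straight after injection. Mild or moderate events later in the visit that nobody charts may be under-counted in a rate the trial sets out to estimate, and failed block cannot be counted consistently without a rule.

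The size of any under-count cannot be derived from the documents. The 6.5% and 9.7% limits rest wholly on assumed capture of 75% and 50%, which is least plausible for the predefined serious events. The primary analysis, the interim rule and the sample size are unaffected. This is an inexpensive improvement to a safety objective.

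**What to change.** 1. In 5.4, 6.2 and 8.2, add to the existing one-hour form a short structured list of the complications named in 8.1 and 8.6.3. Pass positive answers to the physician investigator, for handling under 8.6.4. No post-procedure checklist is described that could be reused (the one in 5.2 is a pre-procedure safety screen), so the list has to be written and should serve both checks.
2. Define in-ED complications as those from injection to ED departure, combining both checks with the chart, and use this window for the immediate complications in 3.6.3.
3. State how failed block is counted, using the one-hour pain score already taken.
4. Extend 8.6.2 so that whoever makes the one-hour contact may record these items.
5. Reconcile 8.2, where the proceduralist reassesses at 60 minutes, with 5.4 and 6.2, where someone else does, and align 5.1, which reads as though the investigator who did the block collects the data. Reconcile 8.6.2, which takes adverse events for those who opt out from the EHR, with 5.5 and 6.3, which give them a day-30 assessment.

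The cost is a short amendment, a few form fields and an estimated 1 to 2 minutes per patient, or 60 to 120 minutes over 60 patients. No new visit or test is needed. The reported complication rate may come out slightly higher.

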# 5.5 Post-emergency department follow up

Follow up assessments will be performed at 1-, 7- and 30-days post emergency department visit. The goal of these brief assessments is to collect data regarding: 1) quality and duration of analgesia related to ESPB; 2) use of other medications for pain and nausea; 3) further treatments and healthcare utilization for kidney stones. Participants in follow up assessments will be compensated with \$10 Amazon.com gift cards or equivalent compensation delivered electronically for each completed assessment which we estimate will take 5-10 minutes or less to complete.

For participants who receive ESPB but do not elect to participate in the optional follow-up, the study team will call the participant at day 30 and assess only for potential adverse events related to ESPB. Participants who did not consent for the optional follow-up will not be asked about pain medication usage, return visits to the ED and other information unrelated to adverse events.

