# 2.10 Sample Size

- This study is a two-stage trial with one planned interim analysis for futility
- Based on the prior 30-month time period (as of May 2022), 572 out of 1071 patients (53.4%) presenting to the ED and meeting the inclusion criteria did not require a 2nd parenteral pain medication during the ED encounter. Thus, we estimate a baseline response rate of 55%.
- Prior work by Nobel et al.¹and Aydin et al.² suggests that no patient will require a second dose of any pain medication after ESPB, but we estimate a conservative response rate of 75% for treatment with ESPB.
- Using Simon's optimal two-stage design with these parameters and  $\alpha$  = 0.05,  $\beta$  = 0.10, we estimate that 18 subjects will be required at the interim analysis and 54 subjects will be required to complete this study.
- Using a Bayesian two-stage design, where interim analysis is planned at one-third total enrollment and a stopping rule if there is only a 10% probability of ESPB demonstrating a 75% response rate, we estimate that 45 total subjects (15 at interim analysis) will be required to achieve a 1.4% chance of stopping early and 95.2% chance of rejecting the null hypothesis.
- This study will aim to achieve a total enrollment of 60 subjects who receive ESPB to account for losses to follow up and withdrawals from the study. Up to 180 (3:1 ratio) historical controls will also be included in the study thus the total enrollment including both treatment and control patients is 240.

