# 6.3 Follow up assessments via web-based survey

At day 1, 7 and 30 after the ED visit, a brief web-based survey will be administered to the participant via E-mail with or without telephone assistance based on the participant's preference. This survey form will assess pain management after the index ED visit, return visits to the ED, and other outpatient follow up or interventions for kidney stones. Each follow up assessment will also evaluate for known complications of ESPB and other adverse events. All follow up assessments are part of the optional sub-study optional except for the assessment of adverse events at day 30.

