#### 8.6.6 Grading, relatedness, and expectedness

The PI or designee will grade each adverse event using a 0 through 5 scale with the following grades:

- 0 No adverse event
- 1 Mild AE No treatment needed
- 2 Moderate AE Resolved with treatment
- 3 Severe AE Inability to carry on normal activities, required professional medical attention
- 4 Life-threatening or disabling AE
- 5 Fatal AE

The PI or designee will also determine the relatedness of any adverse events to study procedures using the following scale:

Definitely related Probably related Possibly related Unlikely to be related Definitely not related

[figure not shown]
The PI or designee will also determine the expectedness of any adverse events to study procedures using the following criteria:

Unexpected adverse events (i.e., has NOT been addressed or described in one or more of the following: Informed consent document(s) for this study, IRB application for this study, grant application or study agreement, protocol or procedures for this study, investigators' brochure or equivalent (for FDA regulated drugs or devices), DSMB/DSC Reports, published literature, other documentation)

Expected adverse events (i.e., has been addressed or described in one or more of the following: Informed consent document(s) for this study, IRB application for this study, grant application or study agreement, protocol or procedures for this study, investigators' brochure or equivalent (for FDA regulated drugs or devices), DSMB/DSC Reports, published literature, other documentation, or characteristics of the study population)

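### The day-30 safety call asks participants who decline the surveys a narrower set of questions, and the protocol contradicts itself on the call's scope and on where their safety data come from

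*Combined protocol and SAP*

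**What the plan says.** Section 5.5 covers ESPB recipients who "do not elect to participate in the optional follow-up, the study team will call the participant at day 30". That call is to assess "only for potential adverse events", and the sentence goes on to restrict these to events related to ESPB. The next sentence says: "Participants who did not consent for the optional follow-up will not be asked about pain medication usage, return visits to the ED". Its closing words, "return visits to the ED and other information unrelated to adverse events", place return ED visits among the non-safety items.

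Survey participants are contacted at days 1, 7 and 30. Section 6.3 has them asked about return ED visits and states: "Each follow up assessment will also evaluate for known complications of ESPB and other adverse events". It then makes every follow-up assessment optional apart from the adverse-event assessment at day 30.

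Section 8.6.3 predefines as serious "2) hospitalization or prolongation of hospitalization as a result of" a procedure complication, and says that all adverse events are logged centrally. Under 8.6.6 the PI or designee "will also determine the relatedness of any adverse events to study procedures", on a scale running from definitely related to definitely not related. Section 8.6.2 says that adverse events in participants who opt out are ascertained from the EHR, that all available data sources are used, and that participants are told how to self-report.

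**The concern.** Day-30 safety and complications are a secondary outcome (3.6.2), and the complication rate is a stated objective (2.3, 3.5). Two features of 5.5 make that rate harder to interpret.

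First, the call is framed by relatedness before the person charged with judging relatedness has seen the event. A participant who does not connect a symptom with the block may not mention it.

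Second, a return ED visit is a natural prompt for recalling a complication or an admission. It is put to survey participants and withheld from the others. Both groups then feed a single day-30 result, although they were asked different questions at different numbers of contacts.

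Complications are expected to be extremely rare (8.1), so the result may rest on zero or one event. With so few events, completeness of ascertainment largely decides what can be concluded.

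**Working it through.** The documents give no complication rate, opt-in rate or safety precision, so there is no plan figure to reproduce. The main check is a comparison of the text.

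**1. Scope of the day-30 contact for participants who decline the surveys**
- 5.1: a telephone call for adverse events only, with no relatedness limit.
- 5.5: potential adverse events related to ESPB only; return ED visits not asked.
- 6.3: each assessment covers ESPB complications and other adverse events, and the day-30 adverse-event part is not optional.
- 2.9: at day 30 only the pain-medication questions are named as optional.
- 8.6.2: the EHR is the stated source for those who opt out; the day-30 call is not mentioned.
- 8.6.3 and 8.6.6: all adverse events are logged, and relatedness is judged afterwards.

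Section 5.5 is the only one that filters on relatedness and the only one that bars the return-visit question. Section 8.6.2 differs from 5.1 and 5.5 on the source.

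**2. What differs by opt-in status.** Under 5.5 as written, three things differ: contacts (days 1, 7 and 30 against day 30 only), event scope (other adverse events against ESPB-related ones) and the return-visit item.

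**3. How an event could be lost.** In a participant who declined the surveys, it must be missed by the call, be absent from the EHR sources in 6.4, and not be self-reported. Care outside the site's EHR that the participant does not link to the block is the plausible case. Whether those sources hold outside care is not stated, so this is an assumption.

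**4. How many return visits might need a cause assigned.** Section 3.1 cites up to one in ten kidney-stone ED patients returning and as many as a third of those being admitted. With the target in 2.10 ("aim to achieve a total enrollment of 60 subjects who receive ESPB"), that is at most about 60 × 0.10 = 6 returns and 6 / 3 = 2 admissions. Most would presumably be due to the stone, but that is known only once each has been recorded.

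**5. Illustration under assumed inputs.** Let q be the opt-in share and s the detection in the remaining participants by all routes combined, relative to survey participants. The relative understatement of the pooled rate is (1 − q)(1 − s). Assumed ranges are q = 25–75% and s = 50–100%.
- s = 1: understatement 0, whatever q is.
- q = 0.75, s = 0.5: 0.25 × 0.5 = 12.5%.
- q = 0.50, s = 0.5: 0.50 × 0.5 = 25%.
- q = 0.25, s = 0.5: 0.75 × 0.5 = 37.5%.

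With an assumed true rate of 2%, the expected number of events is 60 × 0.02 = 1.2, so the largest loss in this range is 1.2 × 0.375 = 0.45 of an event. The chance of recording at least one event, 1 − (1 − 0.02 × [q + (1 − q)s])^60, is 70% with full detection, 60% at q = 0.5 and s = 0.5, and 53% at q = 0.25 and s = 0.5.

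For zero recorded events, the one-sided 95% upper limit is 1 − 0.05^(1/n). This is 4.9% for n = 60. In the extreme case where half opt in and the other half contribute no information, n = 30 and the limit is 9.5%.

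**The case against.** The strongest reply is that the call is not the only safety net. Section 8.6.2 addresses this group directly through the EHR, commits to all available sources and provides for self-report. The 72-hour ED return outcome comes from the EHR for everyone (4.4, 7.4), so it does not depend on the call. Complications and hospitalizations caused by them remain within the call's scope: site infection is a predefined serious event (8.6.3) and pneumothorax is a listed complication (8.1). In 5.5 the return-visit item can be read as a healthcare-utilization question, and sparing people who declined the surveys such questions is a reasonable consent boundary. The call script is not in the documents, and complications are not compared with controls (7.4), so no hypothesis test is touched.

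Most of this stands. A reader might infer that the call cannot find the hospitalizations and complications it exists to find, that a participant treated elsewhere would be recorded as event-free, or that the pooled rate is biased downward by a known amount. The documents support none of these. An event has to escape every route, and s = 1 is compatible with the text.

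The reply does not remove the contradiction between sections. A utilization item can also be a safety prompt: whether a complication caused an admission can be judged only once the admission is known. The consent boundary can be kept for pain medication and satisfaction without extending it to ED visits.

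**Conclusion.** The point holds as one of inconsistent scope and uneven ascertainment. Section 5.5 imposes a relatedness limit and a bar on asking about return visits that 5.1, 6.3, 8.6.3 and 8.6.6 do not share, and 8.6.2 names a different source for the same participants. As written, day-30 safety questions differ by opt-in status.

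The effect on the complication rate cannot be sized from the documents and may be zero. The 0–37.5% relative understatement above depends wholly on assumed values of q and s, and on a 2% event rate it amounts to less than half an event in 60 patients. The primary outcome is not affected. The change is worth making because it is cheap and because a finding of few or no complications is persuasive only if everyone treated was asked the same questions.

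**What to change.** Reconcile 5.1, 5.5, 6.3 and 8.6.2 so that they give the same scope and sources for day-30 safety, with the call named in 8.6.2 alongside the EHR and self-report.

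Use one short day-30 safety question set for every ESPB recipient:
1. Any ED visit or hospitalization, at any institution, since the block, and the reason.
2. The predefined complications.
3. Any other new symptom, whatever its suspected cause.

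Record all answers without a prior relatedness filter and let the PI or designee assign relatedness afterwards under 8.6.6. In 5.5, remove the restriction to block-related events and take return ED visits off the list of items not asked. Pain-medication and satisfaction questions stay optional. Report day-30 events by opt-in status as well as pooled, because the day 1 and day 7 contacts will still differ.

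The cost is an amendment to 5.5 and the related sections, matching consent wording, and an estimated one to two minutes in a call that is already planned. No visit, staff or sample-size change is needed. The downside is a few more questions for people who declined the surveys.
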